2.1. Primary objective

Our main hypothesis is based on the following observations:

- IAC insertion is time consuming and may delay urgent procedures
- IAC insertion is cost consuming
- IAC may lead to complications (infections, thrombosis) and undue blood samplings and transfusions
- NIBP, with an adapted cuff size, can be used safely and reliably to predict MAP < 65 mmHg
- NIBP can be used to track spontaneous or therapy-induced changes in MAP
- Central venous blood analysis combined with SpO₂ offer clinically useful estimation of arterial lactate, arterial pH, PaO₂, PaCO₂ and SaO₂

Therefore, the question arises of whether ICU patients with circulatory failure would not be safely managed without the insertion of an IAC, contrary to what is currently done in common practice.

The objective of the present research is a combination of a one-sided test of non-inferiority and a one-sided test of superiority. A stepped approach will be used to evaluate these hypotheses:

- a) a less invasive intervention (i.e., no IAC insertion until felt absolutely needed, according to consensual and predefined safety criteria [see below]) is non-inferior to usual care (i.e., systematic IAC insertion in the early hours of shock) in terms of mortality at day 28 (non-inferiority margin of 5%).
- b) a less invasive intervention is not only non-inferior but also superior to usual care in terms of mortality

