6.2. Statistical analysis of clinical outcomes

General principles

The statistical analyses will be performed by the INSERM CIC 1415 unit and supervised by [name]. SAS 9.4 and R 3.3 (or further versions) softwares will be used. A detailed analysis plan will be *a priori* defined. Later modifications must occur before unblinding the database. The statistical analysis will be conducted on the per-protocol and intention to treat (ITT) populations as recommended for non inferiority trials. A statistical report will be written in agreement with the standards as specified in the CONSORT Statement and its extension for non pharmacological interventions and for non inferiority trials (<http://www.consort-statement.org/>)

Baseline characteristics

Baseline characteristics will be reported per group using descriptive statistics. No statistical test will be performed.

Groups to be compared

The ITT principle will be applied. Nevertheless, patients who would withdrew consent to study participation will be discarded, as required by the French legislation.

Because patients are ICU patients, it is expected to have no lost-to-follow-up patient. We moreover plan to collect the place of birth, such that we will be able to collect the vital status asking to the city halls. If there are several lost-to follow-up patients, we will use multiple imputation.

The per protocol population will be defined during the blind review.

Statistical analysis of the primary outcome

The between-group difference (experimental group minus usual care group) in rates of day-28 mortality will be estimated based on the 2-sided 95% Confidence Interval (CI). The upper boundary of the 95% CI will be compared with the non inferiority margin of 5%. If non-inferiority is demonstrated, the upper bound of the 95%CI will be compared to 0: if it is lower than 0, then a superiority conclusion will be drawn.(68)

As a sensitivity analysis, we will perform a multivariate logistic regression, to estimate the odds ratio adjusted on the stratification variables.(69)

Statistical analysis of secondary clinical outcomes

- Day-90 mortality: the between-group difference in rates of day-90 mortality will be estimated based on the 2-sided 95% CI.
- Number of patients who underwent IAC insertion, in both groups.

No statistical test will be performed for this outcome, which would be nonsense.

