Deferring arterial catheterization in critically ill patients with shock – EVERDAC trial

STATISTICAL ANALYSIS PLAN — December 2024

The initial Statistical Analysis Plan established before launching the study and published in BMJ Open in 2021 ([name] et al. BMJ Open 2021;11:e044719. doi:10.1136/bmjopen-2020-044719) was amended after the blind review of the data in December 2024.

Level of statistical significance

Statistical significance threshold will be set at 5%, and 95% two-sided confidence intervals (95%CI) will be calculated for all estimates.

Analyzed population

All randomized patients, except for patients who secondarily object to the use of their data or protected under guardianship, will be included in the analysis. No interim analysis will be performed.

Two per-protocol populations were defined during the blind review:

- In the first per-protocol population, we will exclude patients wrongly included, and patients from the noninvasive group in whom the arterial catheter previously inserted was not removed after the randomization. In the invasive group, we will exclude the patients who either did not undergo an attempt at arterial catheter insertion or had the arterial catheter insertion more than 24h after randomization.
- In the second per-protocol population, we will exclude patients from the invasive group who did not receive an arterial catheter within 24h after randomization, regardless of the reason (unsuccessful arterial catheter insertion, no attempt of arterial catheter insertion or insertion occurring more than 24h after randomization). The per-protocol population in the noninvasive group will remain unchanged for the second per-protocol analysis.

Description of baseline characteristics

All data recorded at baseline will be summarized by treatment group using means and standard deviation for normally distributed quantitative variables, median and interquartile range for other quantitative variables, and counts and percentages for qualitative variables. No statistical test will be used.

Primary outcome

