The primary analysis of the primary outcome will be the determination of the between-group difference (noninvasive group minus invasive group) in rates of day-28 mortality, estimated with a binomial generalized estimating equation (GEE) model with identity link adjusted on the stratification variables and on the center effect (Pedroza 10.1186/s12874-016-0217-0). A switch from noninferiority to superiority is *a priori* planned if the hypothesis of noninferiority with a noninferiority margin of 5 percentage points is verified. These hypotheses will be assessed using the stratified Farrington-Manning test for differences in proportions.

Secondary outcomes analysis

Statistical analyses for secondary outcomes will not be adjusted for multiplicity; therefore, secondary-outcome findings should be interpreted as exploratory.

- Day-90 mortality will be analyzed with the same model as the primary outcome .
- Cumulative incidence of death from randomization through Day 90 will be analyzed with a Cox model.
- ICU mortality and hospital mortality will be analyzed in a competing risks framework. A hazard ratio will be computed from the whole groups using a Fine and Gray regression model. ICU discharge or hospital discharge will be considered as competing events.

The following outcomes will be described with median and quartiles and compared between groups using median differences:

- Duration of ICU stay from randomization to discharge.
- Duration of hospital stay from randomization to discharge.
- Duration of mechanical ventilation from randomization and Day 28.
- Ventilator-free days from randomization to Day 28.
- Renal replacement therapy-free days from randomization to Day 28.
- Vasopressor therapy-free days from randomization to Day 28.

For each outcome, 95% confidence intervals of the median difference will be computed using unstratified bootstrapping (10,000 samples with replacement). Vasopressor therapy-free days, renal replacement therapy-free days and duration of mechanical ventilation do not account for the competing risk of death.

The following outcomes will be represented with boxplots at each day:

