Patient-reported pain and discomfort related to the device used for BP monitoring will be measured daily using 4 scales rating from 0 to 10. Each day, a patient will be considered as experiencing pain and/or discomfort if at least one scale is ≥ 4 (Gerbershagen, DOI: 10.1093/bja/aer195). The proportions of patients experiencing at least one day with pain and/or discomfort will be compared with a chi-squared test. The numbers of days with pain and/or discomfort will be compared between the groups with the use of a quasi-Poisson regression model and expressed as rate ratios, with the duration of stay in the ICU as the offset.

- The number of patients reaching the predefined upper limit of vasopressor dosage ($>2.5\mu\text{g}/\text{kg}/\text{min}$ of norepinephrine tartrate plus epinephrine) will be estimated in each group, and day 28 mortality will be described amongst these severely ill patients.

Subgroup analyses

No subgroup analyses were prespecified.

Implementation

Statistician: [name] , Centre d'Investigation Clinique INSERM 1415, CHRU de Tours.

Software: R version 4.3.1

SUMMARY OF CHANGES FROM THE INITIAL PROTOCOL AND JUSTIFICATIONS

Changes in the analyses of the primary outcome

Additional methodological recommendations were identified on current recommendations to estimate a difference in proportions (Pedroza 10.1186/s12874-016-0217-0), recommendations on adjusting stratification variables (Sullivan 10.1002/sim.10060) and recommendations on taking account of the center effect for multicenter studies (Kahan 2013 10.1002/sim.5667, Pedroza 10.1186/s12874-016-0217-0). The final GEE model was established during the analysis of the data, as we observed a significant within-center correlation (Intra-class correlation coefficient = 0.02 for day 28 mortality in each group).

To quantify how strongly our data reject the possibility that the true difference exceeds the 5% noninferiority margin, we employed a stratified Farrington–Manning test. This approach formally tests the noninferiority hypothesis and complements the estimation of the between-group difference obtained with the GEE model. This decision was made during the analysis of the data.

Changes in the analyses of the secondary outcomes

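### Does the SAP's 5% threshold leave open the level at which the Farrington-Manning non-inferiority test is read?

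*SAP*

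**What the plan says.** Protocol section 2.1 sets the direction of the tests: "The objective of the present research is a combination of a one-sided test of non-inferiority and a one-sided test of superiority". Section 6.1 gives a margin of 5%, power of 80% and an alpha risk of 5%, with no sidedness, and plans 1010 patients.

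Protocol section 6.2 (Statistical analysis of the primary outcome) gives the working rule, based on a two-sided 95% confidence interval for the mortality difference, experimental minus usual care. For non-inferiority: "The upper boundary of the 95% CI will be compared with the non inferiority margin of 5" per cent. If that succeeds, "the upper bound of the 95%CI will be compared to 0: if it is lower than 0, then a superiority conclusion will be drawn".

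The SAP (Level of statistical significance) says: "Statistical significance threshold will be set at 5%, and 95% two-sided confidence intervals (95%CI) will be calculated for all estimates". Under Primary outcome, a GEE model estimates the difference. A switch to superiority is planned "if the hypothesis of noninferiority with a noninferiority margin of 5 percentage points is verified", and then: "These hypotheses will be assessed using the stratified Farrington-Manning test for differences in proportions". No p-value cut-off is attached to that test.

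The SAP's summary of changes explains that the test was added "To quantify how strongly our data reject the possibility that the true difference exceeds the 5% noninferiority margin", and continues: "This approach formally tests the noninferiority hypothesis and complements the estimation of the between-group difference obtained with the GEE model". It dates this choice to the analysis of the data.

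**The concern.** Three statements together allow an unintended reading. The protocol calls the tests one-sided, section 6.1 puts alpha at 5%, and the SAP's 5% carries no sidedness, since two-sided there qualifies only the intervals. A non-inferiority p-value is directional, so someone working from these lines alone could compare a one-sided Farrington-Manning p-value with 0.05.

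The primary conclusion and the switch to superiority both depend on that cut-off. At one-sided 0.05 the false-positive rate would be twice the level the trial was sized on, and non-inferiority could be declared while the reported 95% interval crosses the margin.

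A related question is precedence. The SAP does not say whether the Farrington-Manning test replaces the interval rule of section 6.2, or what follows if the test and the GEE interval disagree.

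**Working it through.** **1. Reproduce the sample size.** Inputs from protocol section 6.1: mortality 22.5% (experimental) and 25% (control), margin 5 points, power 80%. Allocation is 1:1 (section 4), with no inflation for loss to follow-up (section 6.2 expects none).

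n per arm = (z₁₋α + z₀.₈)² × [p₁(1−p₁) + p₀(1−p₀)] / (margin − expected difference)²

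- Variance term: 0.225×0.775 + 0.25×0.75 = 0.361875.
- Denominator: (0.05 + 0.025)² = 0.005625.
- One-sided 2.5%: (1.960 + 0.842)² × 0.361875 / 0.005625 = 504.9, so 505 per arm and **1010 in total**, the planned figure.
- One-sided 5%: (1.645 + 0.842)² × 0.361875 / 0.005625 = 397.7, so 398 per arm and **796 in total**.

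With the Farrington-Manning restricted variance the totals are 1014 and 800. The design level is one-sided 2.5%.

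**2. Compare with the stated rule.** Requiring the upper limit of a two-sided 95% interval to lie below a value is a one-sided 2.5% test against that value. Section 6.2 applies this to 5 points and then to 0, so both hypotheses have the level found in step 1.

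**3. What the other reading would cost.** Exact binomial enumeration, 505 per arm, unstratified, no centre correlation. FM is the Farrington-Manning test, read one-sided.

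| True mortality, experimental vs control | Conclusion | Wald 95% CI | FM at 0.025 | FM at 0.05 |
|---|---|---|---|---|
| 30% vs 25% | non-inferior | 2.5% | 2.5% | 5.0% |
| 25% vs 25% | non-inferior | 45.2% | 45.1% | 57.6% |
| 22.5% vs 25% | non-inferior | 80.1% | 80.0% | 87.6% |
| 25% vs 25% | superior | 2.5% | 2.5% | 5.0% |
| 22.5% vs 25% | superior | 15.3% | 15.3% | 23.9% |

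The non-inferiority verdict differs between the two cut-offs in 12.5% of trials at 25% vs 25% (57.6 − 45.1) and in 7.7% at the planned rates.

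**4. Where the verdict would change.** Take 126 deaths among 505 controls.

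| Noninvasive deaths | Hypothesis | One-sided p | Upper 95% limit (points) |
|---|---|---|---|
| 124 | non-inferiority | 0.0236 | 4.93 |
| 125 | non-inferiority | 0.0281 | 5.13 |
| 128 | non-inferiority | 0.0459 | 5.75 |
| 129 | non-inferiority | 0.0536 | 5.95 |
| 100 | superiority | 0.0248 | −0.02 |
| 101 | superiority | 0.0297 | 0.19 |
| 104 | superiority | 0.0494 | 0.81 |
| 105 | superiority | 0.0578 | 1.02 |

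Only 125 to 128 deaths (non-inferiority) and 101 to 104 deaths (superiority) pass at 0.05 but not at 0.025. In each of these cases the two-sided 95% interval, which the SAP requires for every estimate, contains the value that had to be excluded.

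**5. Test against interval at the same level.** Unstratified, the Wald 95% interval and the test at one-sided 0.025 disagree in about 0.1% of trials or fewer. In a simulation of the stratified test against the GEE interval (1010 patients, 11 centres, intra-class correlation 0.02, 25% mortality in both arms, 2000 trials per setting), disagreement was:

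- 1.3–8.2% with model-based standard errors, for assumed covariate effects of 0 to +10 points;
- 14.3–15.5% with model-based standard errors at +15 points;
- 12.6–16.5% with uncorrected robust standard errors, for effects of 0 to +10 points.

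The simulation also assumed 60% ventilated, 52% on the higher vasopressor dose, and a set of centre sizes. None of these is in the documents.

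**The case for a change.** The best case for a change is that the Farrington-Manning test was chosen during the analysis of the data. A test added that late should carry an explicit threshold, so that nobody can suspect the cut-off was picked after the results were seen. The protocol does use the words one-sided and 5%, the SAP does not repeat the interval rule, and two extra sentences would cost no patients and leave power at the planned 80%.

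The omission is real: neither document writes 2.5% or a p-value cut-off for this test. The inference from it is weaker. One-sided in section 2.1 describes direction, and section 6.2 supplies the level. The SAP's remark about exceeding the margin is equally uninformative, since every non-inferiority test is directional. A claim made at one-sided 0.05 would also normally show against the reported 95% interval, as step 4 illustrates without adjustment.

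On precedence, the SAP does not rank the two methods. It does say the test complements the GEE estimation, and its summary of changes does not record the interval rule as dropped. The larger disagreement rates come from assumed covariate effects, centre sizes and standard-error choices, not from missing sidedness. They show that the methods can differ, but not that the plan leads to a wrong answer.

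**Conclusion.** No change is needed. The SAP does not restate the level beside the new test, but the interval rule in protocol section 6.2, the two-sided 95% intervals in the SAP's significance sentence, and the sample size of 1010 all give one-sided 2.5%, equivalent to two-sided 5%. An analyst who follows them reads the test at 0.025 for both hypotheses, with 2.5% false non-inferiority at the margin and 80.0% power at the planned rates. Writing the level down would record what is already implied without altering the analysis.

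The doubled error rate and the 12.5% of changed verdicts are conditional on comparing a one-sided p-value with 0.05, which no part of either document states. They also assume 505 per arm without stratification or centre correlation. Precedence between the test and the GEE interval is a reporting detail: with both results shown, any disagreement is visible to the reader, and its likely frequency cannot be fixed from the documents.

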 - OR requirement of continuous iv vasopressor treatment (i.e. noradrenaline tartrate at a dose $\geq 0,2 \mu\text{g}/\text{kg}/\text{min}$ or any dose of epinephrine) for more than 4 hours
- AND at least one of the following signs of hypoperfusion: alteration of mental status; skin mottling; oliguria defined as a urine output $< 0.5 \text{ mL/kg body weight}$ for at least one hour; arterial lactate $> 2 \text{ mmol/L}$; peripheral venous lactate $> 3.2 \text{ mmol/L}$; $\text{ScvO}_2 < 70\%$

b) **“non-invasive care”:** No IAC insertion will be allowed during the first 28 days, excepted if predefined safety criteria (indicating absolute need of IAC insertion) are reached (see below): IAC will be inserted within the 4 hours of presence of safety criteria and patient will be managed as if he/she were part of usual care group until day 28 or ICU discharge. Arterial blood draw is allowed via direct arterial puncture as frequently as indicated.

Criteria of IAC futility (one or more criteria defined futility) allowing IAC removal at physician’s discretion:

- The patient no longer needs significant vasopressor therapy (i.e. no longer needs norepinephrine tartrate at a dose $\geq 0,2 \mu\text{g}/\text{kg}/\text{min}$ or any dose of epinephrine) for more than 4 hours, and exhibits no sign of hypoperfusion (i.e., neither alteration of mental status, skin mottling, oliguria defined as a urine output $< 0.5 \text{ ml/kg body weight}$ for at least one hour, arterial lactate $> 2 \text{ mmol/L}$, peripheral venous lactate $> 3.2 \text{ mmol/L}$ or $\text{ScvO}_2 < 70\%$)
- Medical decision of palliative care

Safety criteria for IAC insertion for patients initially randomized in the “no-IAC” group:

As undisputable criteria are lacking in the medical literature, criteria were consensually determined (Delphi method) after collecting the opinion of the anticipated investigators (senior ICU physicians) in each centre. After two turns of notation, the following criteria were retained (since the median of notation fell between 7 and 9 on a 9-point scale; extending from score 1 [“do not agree at all”] to score 9 [fully agree]) with low

- Although the pulse oximetry monitor was working well at inclusion, it can no longer display any reliable SpO₂ value
- Despite NIBP readings were available at inclusion, NIBP now consistently fails to display any reliable BP value

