We deliberately decided not to perform a cluster-randomized trial. This design is prone to the risk of selection bias. Moreover, there are few centres in the study, which could lead to chance imbalance.

As the need for IAC insertion is rooted in intensivists' mind when caring for patients in shock, there is a real risk that patients assigned to the non-invasive arm will frequently be switched to the invasive arm (with IAC insertion). To prevent this kind of contamination bias, the study scientific committee has set reasonable and consensual safety boundaries that will fix in which circumstances the insertion of an IAC will become an inescapable need (in terms of vasopressor requirement for instance [see the "3. *Interventions*" paragraph]). In the end, we opted for a classical standard individually randomised trial and worked at limiting group contamination.

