4.7. Measures taken to minimise or avoid bias

Recruitment

All patients admitted in the participating ICUs during the study period will be screened for eligibility. Investigators will make every effort to include all consecutive eligible patients to avoid selection bias. Investigators and study personal at each centre will fill in a screening-log form in which will be recorded included and non included eligible patients' characteristics (age, gender, Simplified Acute Physiology score [SAPS II](67), cause of shock, ICU survival, cause of non inclusion if applicable) to allow assessing the representativeness of the study population and drawing conclusions concerning the generalizability of the results.

Randomisation

Randomisation is mandatory to minimise selection bias.

Stratification

Stratification on centres, invasive mechanical ventilation and vasopressor dosage at time of enrolment is planned to have well balanced groups concerning the general care approach (which could differ between centres).

Definition of safety criteria for IAC insertion in the experimental group

The study scientific committee has set reasonable and consensual safety boundaries that will fix in which circumstances the insertion of an IAC will become an inescapable need. Doing so will contribute to limiting group contamination which would occur if too many patients from the experimental group had an IAC.

Choice of the primary outcome measure

As blinding of investigators and of all ICU staff members is not technically feasible, we chose a "hard" endpoint (Day-28 mortality) to minimise bias.

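### Should the per-protocol sets drop noninvasive patients who were catheterised with no safety criterion met?

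*SAP*

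**What the plan says.** Protocol section 3 (Interventions) sets the rule for the noninvasive arm: "No IAC insertion will be allowed during the first 28 days, excepted if predefined safety criteria (indicating absolute need of IAC insertion) are reached". Once a criterion is met and a catheter is placed, the "patient will be managed as if he/she were part of usual care group until day 28 or ICU discharge", so catheters placed on a criterion are part of the assigned strategy.

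Section 4 (Study design) says "there is a real risk that patients assigned to the non-invasive arm will frequently be switched to the invasive arm". Section 4.7 presents the safety criteria as the countermeasure: "Doing so will contribute to limiting group contamination which would occur if too many patients from the experimental group had an IAC".

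Section 6.2 states: "The statistical analysis will be conducted on the per-protocol and intention to treat (ITT) populations as recommended for non inferiority trials". It leaves the per-protocol definition to the blind review.

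The SAP (Analyzed population) reports two sets from that review. In the noninvasive arm the first set drops wrongly included patients and "patients from the noninvasive group in whom the arterial catheter previously inserted was not removed after the randomization". In the invasive arm it drops those with no insertion attempt and those who "had the arterial catheter insertion more than 24h after randomization". The second set is stricter in the invasive arm only: "The per-protocol population in the noninvasive group will remain unchanged for the second per-protocol analysis".

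**The concern.** Neither set refers to the safety criteria. A noninvasive patient catheterised with none of them met has broken the arm's central rule, yet counts as per-protocol in both sets. Below, this is called an off-criteria insertion.

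In a non-inferiority trial, switching of this kind draws the arms together. If the noninvasive strategy is truly worse, that makes a false claim of non-inferiority easier. A per-protocol analysis is normally run to expose such dilution. Here both sets share it with the all-randomised analysis, so agreement among the three would say little about this form of contamination.

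The rest of the plan does not isolate it either. The proportion catheterised (protocol 6.2), and the insertion counts and cumulative incidence curves (SAP, Secondary outcomes analysis), do not split insertions by whether a criterion was met. The SAP's additional safety analysis covers the vasopressor criterion alone.

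**Working it through.** **Inputs.** Protocol 6.1: day-28 mortality 25% (control) and 22.5% (experimental), margin 5 points, power 80%, 1010 patients. Protocol 6.2: non-inferiority is judged on the upper limit of a two-sided 95% interval, which is one-sided 2.5%. Section 4: 1:1 allocation. The off-criteria share *c* of the noninvasive arm is given nowhere, so 5% to 30% is assumed.

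**1. The plan's own figure.** n per arm = (1.960 + 0.842)² × (0.225×0.775 + 0.25×0.75) / (0.05 + 0.025)² = 7.849 × 0.361875 / 0.005625 = 504.9, so 505 per arm and 1010 in total. It reproduces exactly. One-sided 5% would give 398 per arm, or 796.

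**2. Keeping the switched patients.** Suppose full adherence to the noninvasive strategy gives 30% mortality against 25%, exactly at the margin. Let an off-criteria catheter remove a fraction *k* of the harm. Then:

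- p1 = 0.25 + 0.05(1 − kc) and d = p1 − 0.25
- SE = √[p1(1−p1)/n1 + 0.25×0.75/505], with n1 = 505
- P(non-inferiority) = Φ((0.05 − d)/SE − 1.96)

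Example, c = 10% and k = 1: p1 = 0.295, SE = 0.02798, Φ(0.179 − 1.96) = 3.7%.

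**3. Excluding them.** If the switched patients have mortality *m*, then p1 = (0.25 + 0.05(1−c) − cm)/(1−c) and n1 = 505(1−c), with k = 1. Example, c = 10% and m = 35%: p1 = (0.295 − 0.035)/0.9 = 0.2889, SE = 0.02869, Φ(0.387 − 1.96) = 5.8%.

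**4. Power under the protocol's assumption.** With k = 1, p1 = 0.25 − 0.025(1−c) and n1 = 505.

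| c (patients of 505) | False NI, kept, k=1 | False NI, kept, k=½ | Break-even m, k=1 | Arm average, k=1 | Power at 22.5% vs 25% |
|---|---|---|---|---|---|
| 0 | 2.5% | 2.5% | – | 30% | 80.0% |
| 5% (25) | 3.1% | 2.8% | 29.8% | 29.75% | 78.6% |
| 10% (51) | 3.7% | 3.1% | 29.6% | 29.5% | 77.1% |
| 20% (101) | 5.5% | 3.7% | 29.3% | 29.0% | 74.1% |
| 30% (152) | 7.8% | 4.5% | 28.9% | 28.5% | 70.8% |

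Break-even m is the mortality among switched patients above which excluding them gives more false non-inferiority than keeping them. It lies just above the arm average, because removing patients of average mortality leaves the arm's rate unchanged.

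False non-inferiority when they are excluded:

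- c = 5%: 2.5%, 3.8% and 4.6% at m = 25%, 35% and 40% (kept: 3.1%).
- c = 10%: 2.5%, 5.8% and 8.4% at the same m (kept: 3.7%).
- c = 20%: 2.5%, 6.2% and 13.4% at m = 25%, 30% and 35% (kept: 5.5%).

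Exclusion restores 2.5% only at m = 25%, that is, when switching is unrelated to prognosis. It also widens the interval: the 95% half-width at p1 = 30% goes from 5.5 points to 5.6, 5.7, 5.9 and 6.1 as c goes from 5% to 30%.

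**The case for a change.** The strongest argument for a change is that the protocol names this contamination as a real risk and promises a per-protocol analysis because the trial tests non-inferiority, yet both sets leave it untouched. The invasive arm is filtered in two ways and the noninvasive arm in one. Exclusion would also help in part of the range: at 10% switching it does better than retention while mortality among the switched patients lies between 25% and 29.6%. A supportive analysis labelled as added after the blind review would cost little, and the SAP already dates several late changes.

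The reading of the two sets stands, and so does the limit on what their agreement can show. The remedy is weaker. Clinicians who place a catheter against the protocol plausibly do so in patients who are deteriorating, which is where exclusion does worse than retention. Adjusting for stratification variables or baseline severity cannot remove selection on what happens after randomisation.

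The added set may not be buildable either. The schedule in protocol section 4.6 lists insertion and removal but not the reason, and some criteria rest on the physician's judgement.

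The sets are also not blind to contamination in general. They remove noninvasive patients whose existing catheter stayed in, which matters because section 4.3 lets patients already carrying one be randomised.

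A related point is separate and not quantified here. The sets tolerate first insertion up to 24 hours and give no limit for removal, while the protocol gives four hours (section 3) and one hour (section 4.3). Section 6.2 left such tolerances to the blind review.

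**Conclusion.** No change to the plan follows. The two sets do keep off-criteria insertions, but no stated rule or figure is wrong: the definition was delegated to the blind review, and the protocol's declared answer to switching was a design measure, the safety criteria, rather than a particular analysis set.

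The effect is of unknown size and its direction depends on the truth. It favours non-inferiority only if the noninvasive strategy is really worse. With a true 5-point harm, false non-inferiority at 5% switching is 2.8% to 3.1%. It reaches 7.8% only if 30% switch and the catheter cancels the entire harm, which is an upper bound. If the strategy is better, as the protocol assumes, switching works against the sponsor through lost power.

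Excluding these patients exchanges dilution for selection bias that can be larger in the same direction (13.4% against 5.5% at 20% switching and 35% mortality). These figures rest on assumed switching rates and mortalities and on a normal approximation with 505 per arm.

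If reasons for insertion were recorded, a descriptive count of off-criteria insertions with their day-28 mortality, classified blind to vital status, would help readers. It would alter no planned result.
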